## 2 PROTOCOL SYNOPSIS

Title	A Phase 3, Open-label Study Evaluating the Long-term Safety of VX-445 Combination Therapy in Subjects With Cystic Fibrosis
Brief Title	A Study Evaluating the Long-term Safety of VX-445 Combination Therapy
Clinical Phase and Clinical Study Type	Phase 3, safety
Objectives	
Primary Objective
 
To evaluate the long-term safety and tolerability of VX-445/tezacaftor (TEZ)/ivacaftor (IVA)

Endpoints	
Primary Endpoint
 
Safety and tolerability of long-term treatment with VX-445/TEZ/IVA based on adverse events (AEs), clinical laboratory values, ECGs, vital signs, pulse oximetry, and spirometry
 
Other Endpoint
 
Sweat chloride

Number of Subjects	Over 400 subjects are expected to enroll in this study.
Study Population	Male and female subjects with cystic fibrosis who are 12 years of age or older and homozygous or heterozygous for the F508del mutation
Investigational Drug	
Study drug refers to VX-445/TEZ/IVA and IVA.
 
Study drugs will be orally administered as 2 fixed-dose combination film-coated tablets (VX-445/TEZ/IVA) in the morning and as 1 film-coated IVA tablet in the evening.
 
Active substance: VX-445, TEZ (VX-661), and IVA (VX-770)
 
Activity: VX-445 is a CFTR corrector, TEZ is a CFTR corrector, and IVA is a CFTR potentiator (increased Cl secretion)
 
Strength: 100 mg/50 mg/75 mg FDC tablet
 
Active substance: IVA (VX-770)
 
Activity: CFTR potentiator (increased Cl secretion)
 
Strength: 150 mg

Study Duration	The total study duration is up to approximately 100 weeks (from the first dose of study drug in this study), including a Treatment Period of up to 96 weeks and a 4-week Safety Follow-up Period.

**Study Design** This is a Phase 3, multicenter, open-label study for subjects in Study 659-105, a Phase 3 Vertex study investigating VX-659/TEZ/IVA, who meet eligibility criteria. All subjects will receive the triple combination of VX-445/TEZ/IVA at the same dose level as that evaluated in the VX-445 Phase 3 pivotal trials.

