## **11.4 Safety**

Safety evaluations will include AEs, clinical laboratory assessments, and clinical evaluation of ECGs, vital signs, height, weight, pulse oximetry, physical examinations (PEs), spirometry, and ophthalmologic examinations. Ophthalmologic examinations will be conducted only on subjects who were <18 years of age on the date of informed consent in the parent studies of Study 659-105.

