## **8 STATISTICAL ANALYSIS**

### **8.1 General Considerations**

In general, data will be summarized by the treatment group in this study.

The precision standards for reporting safety variables are provided in an internal Biometrics document that specifies the programming rules including the precision for derived variables.

**Continuous variables** will be summarized using the following descriptive summary statistics: the number of subjects (n), mean, standard deviation (SD), median, minimum value (min), and maximum value (max).

**Categorical variables** will be summarized using counts and percentages. Percentages will be presented to 1 decimal place.

**Baseline value**, unless otherwise specified, for the long-term safety analysis is defined as the most recent non-missing measurement (scheduled or unscheduled) collected before the first dose of ELX/TEZ/IVA in Part A of this study.

Baseline of sweat chloride is defined as the most recent non-missing sweat chloride (scheduled or unscheduled) collected before the first dose of VX-659 in VX17-659-102 or VX17-659-103 studies.

**Absolute change** from baseline will be calculated as post-baseline value - baseline value.

**Relative change** from baseline will be calculated as  $100\% \times (\text{post-baseline value} - \text{baseline value}) / \text{baseline value}$ .

**Treatment-emergent (TE) Period** for Part A will include the time from the first dose of study drug in Part A to 28 days after the last dose date of the study drug in Part A or to the completion date of study participation in Part A (Section 9.1.5 of the CSP), whichever occurs first.

**Treatment-emergent (TE) Period** for Part B will include the time from the first dose of study drug in Part B to 28 days after the last dose date of the study drug in Part B or to the completion date of study participation in Part B (Section 9.1.5 of the CSP), whichever occurs first.

The completion date of study participation will be obtained from the end of study page of the eCRF for each part respectively.

For subjects who participate in another qualified Vertex study before completing Study VX18-445-113 and resume participation in Study VX18-445-113, the TE Period for either Part A or B will exclude the time spent in the other study.

**Unscheduled visits:** Unscheduled visit measurements will be included in analysis as follows:

- 1) In scheduled visit windows per specified visit windowing rules

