### **8.4 Safety Analysis**

The primary objective of the study is the evaluation of the long-term safety and tolerability of ELX/TEZ/IVA. Safety analysis will be summarized separately for Parts A and B. Part A safety analyses will be based on the TE Period for Part A for subjects in the Safety Set for Part A. Part B safety analyses will be based on the TE Period for Part B for subjects in the Safety Set for Part B. The overall long-term safety profile of study drug will be assessed in terms of the following safety and tolerability endpoints:

- Treatment-emergent adverse events (TEAEs)
- Clinical laboratory values (i.e., serum chemistry, hematology, coagulation, and urinalysis)
- ECGs
- Vital signs including body weight and BMI
- Pulse oximetry
- Spirometry

Only descriptive analysis of safety will be performed, and no statistical testing will be performed.

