### **8.4.4 Vital Signs**

Summaries of vital sign values will be provided separately for Parts A and B based on the Safety Set.

For the vital sign measurements during the TE period for the Safety Set for the corresponding part, the observed values and change from baseline values will be summarized at each visit separately for Parts A and B. The following vital signs parameters will be summarized: BMI ( $\text{kg}/\text{m}^2$ ), weight (kg), systolic and diastolic blood pressure (mm Hg), body temperature ( $^{\circ}\text{C}$ ), pulse rate (beats per minute), and respiratory rate (breaths per minute).

The number and percentage of subjects meeting at least 1 threshold analysis criterion during the TE period for the corresponding part will be summarized separately for Parts A and B. The threshold analysis criteria are provided in [Appendix D](#).

In addition, a listing containing individual subject vital sign values will be provided separately for Parts A and B. This listing will include data from both scheduled and unscheduled visits.

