**Table 11-6 Threshold Analysis Criteria for Vital Signs**

Parameter	Threshold Analysis	Comments	
DBP increased	>90 mmHg		
	>100 mmHg		
	>5 mmHg increase from baseline		
	>10 mmHg increase from baseline		
	>90 mmHg and >5 mmHg increase from baseline		
	>90 mmHg and >10 mmHg increase from baseline		
	>100 mmHg and >5 mmHg increase from baseline		
	>100 mmHg and >10 mmHg increase from baseline		
	DBP decreased	<60 mmHg	
		<45 mmHg	
		>5 mmHg decrease from baseline	
		>10 mmHg decrease from baseline	
		<60 mmHg and >5 mmHg decrease from baseline	
		<60 mmHg and >10 mmHg decrease from baseline	
Weight	<45 mmHg and >5 mmHg decrease from baseline		
	<45 mmHg and >10 mmHg decrease from baseline		
	<45 mmHg and >5 mmHg decrease from baseline		
	<45 mmHg and >10 mmHg decrease from baseline		
	Weight gain	CTCAE grade 1-3	
	≥5 % increase from baseline		
≥10 % increase from baseline			
≥20% increase from baseline			
Weight	Weight loss	CTCAE grade 1-3	
	≥5 % decrease from baseline		
	≥10 % decrease from baseline		
	≥20% decrease from baseline		

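### The weight thresholds and raw weight/BMI change pool growing adolescents with adults, so expected growth counts as weight gain and no visible summary flags stalled growth

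*SAP*

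**What the plan says.** The population in the protocol synopsis is "Male and female subjects with cystic fibrosis who are 12 years of age or older". Minors are expected: Protocol 11.4 plans an eye examination only for those "who were <18 years of age on the date of informed consent in the parent studies of Study 659-105". Neither document says how many there are.

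Vital signs belong to the primary safety endpoint (Protocol 7.1, SAP 5.1), and SAP 8.4 specifies "Vital signs including body weight and BMI". The weight criteria in SAP Table 11-6 are "≥5 % increase from baseline" and "≥5 % decrease from baseline", each followed by 10% and 20% levels and labelled "CTCAE grade 1-3". None has an age qualifier.

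SAP 8.4.4 states: "The number and percentage of subjects meeting at least 1 threshold analysis criterion during the TE period for the corresponding part will be summarized". It also summarises observed values and change in weight (kg) and BMI at each visit. SAP 8.1 sets the grouping: "In general, data will be summarized by the treatment group in this study". There is a single cohort (SAP 6.3), so all ages fall into one column. SAP 8.2.2 lists age without categories.

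SAP 8.1 fixes baseline before the first dose in Part A, for Part B as well. Part B adds 48 weeks and is offered in Australia, Canada, Spain and Poland (SAP 6.1).

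**The concern.** A percentage change in body weight means different things in an adult and in a 13-year-old. In an adult, a 5% gain is a change from a roughly steady state. In a growing adolescent it may be ordinary growth over the follow-up period. In a randomised trial the growth would fall on both arms and largely cancel in the comparison. Here there is no second arm, so the reported percentage mixes growth with any other gain.

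The loss criteria have the opposite problem. They require a fall below the subject's own baseline, so an adolescent who should be gaining and is not shows 0% and meets none of them.

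The plan allows for growth elsewhere. Height is repeated in subjects who consent by age 21 (Protocol 11.4.4), and the percent-predicted spirometry values use visit-specific height in that group (SAP Appendix F). Protocol 13.1.1.4 warns that paediatric ranges may depart from CTCAE, but only for laboratory parameters. The weight criteria, labelled as CTCAE grades, carry no such allowance.

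At stake is the reading of the weight tables within the primary safety endpoint. The analysis is descriptive, so no error rate or power is affected.

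**Working it through.** **Plan's own figures.** The plan states no figure for weight change or growth. Its one statistical figure, ruling out adverse events with a frequency above 1% when none is seen in over 400 subjects, is not an input here.

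**Inputs from the documents.** Thresholds of 5%, 10% and 20% (Table 11-6); treatment of up to 96 weeks (Protocol 9.3.2); 48 further weeks in Part B from the Part A baseline (SAP 6.1, 8.1).

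**Assumptions.** Baseline weight 40 to 55 kg and steady growth of 2 to 5 kg a year.

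**Time.** 24 weeks = 24 × 7/365.25 = 0.46 years; 96 weeks = 1.84 years; 144 weeks = 2.76 years.

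**Growth at Week 96.** Change (%) = 100 × rate × 1.84 / baseline weight.

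| Baseline | 2 kg/yr | 3 kg/yr | 4 kg/yr | 5 kg/yr |
|---|---|---|---|---|
| 40 kg | 9.2 | 13.8 | 18.4 | 23.0 |
| 50 kg | 7.4 | 11.0 | 14.7 | 18.4 |
| 55 kg | 6.7 | 10.0 | 13.4 | 16.7 |

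- All 12 cells reach 5%.
- The nine cells at 3 kg/yr or more reach 10%; none does at 2 kg/yr.
- One cell reaches 20%. At 5 kg/yr the gain is 9.2 kg, so 20% requires a baseline of at most 9.2/0.20 = 46 kg. At 4 kg/yr it requires at most 7.36/0.20 = 36.8 kg, below the assumed range.

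**Growth at Week 24.** Lowest: 2 × 0.46/55 = 1.7%. Highest: 5 × 0.46/40 = 5.75%, about 5.8%. Most combinations stay under 5%. The 5% line is crossed after 0.05 × weight/rate years: 0.40 years (21 weeks) for 40 kg at 5 kg/yr, and 1.375 years (72 weeks) for 55 kg at 2 kg/yr.

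**Part B.** With the Part A baseline, a subject who grew through Week 96 at these rates already carries 6.7% to 23% and can meet the 5% criterion at the first Part B measurement. If growth continues to 144 weeks, the range is 2 × 2.76/55 = 10.0% to 5 × 2.76/40 = 34.5%.

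**Stalled growth.** A 40 kg adolescent who gains nothing over 96 weeks has a change of 0% and meets no criterion. The expected weight would be 43.7 kg at 2 kg/yr or 49.2 kg at 5 kg/yr, a shortfall of 3.7/43.7 = 8% to 9.2/49.2 = 19%. The first loss criterion needs a fall of 2 kg.

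**Does raw BMI settle it?** Only in part. Suppose height goes from 150 to 156 cm (assumed), a factor of 1.04. A 20% weight gain then gives BMI 1.20/1.04² = 1.109, or +10.9%. Unchanged weight gives 1/1.04² = 0.925, or −7.5%. BMI moves in the right direction, but Table 11-6 has no BMI threshold, and the pooled mean change mixes such a subject with adults.

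**Pooled percentage.** If 15% to 30% of 400 subjects were growing adolescents (60 to 120, assumed) and every one were flagged, they would supply 15 to 30 percentage points of the 5% gain row. That is a ceiling. If 70% were flagged, it would be 0.70 × 15 = 10.5 to 0.70 × 30 = 21 points.

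**The case against.** The strongest reply has four parts.

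**Size.** A reader might infer that growth alone carries adolescents past every threshold, or that it adds 15 to 30 percentage points to the 5% row. The documents support neither. Under the assumed rates the 20% level is nearly out of reach and 10% is not always met. The 15 to 30 points need an assumed adolescent share, growth in every one of them, enough follow-up to cross the line, and no gain of 5% for another reason. Some under 18 may have nearly finished growing. Subjects also arrive through a parent study and then Study 659-105, so they are older than at first consent. Treatment is up to 96 weeks, and subjects may leave for commercial drug (Protocol 9.9). All of this stands.

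**Detection.** A reader might infer that failure to grow would go unseen. That is too strong. Weight is measured at most clinic visits, height is repeated in younger subjects, BMI is summarised, individual vital signs are listed (SAP 8.4.4), clinically significant worsening is recorded as an adverse event (Protocol 13.1.1.2), and the IDMC reviews safety data. What remains is narrower: no threshold or visible planned summary flags it.

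**Attribution.** A reader might expect an age split to isolate a drug effect. It cannot: there is no control arm, and subjects come from a study of VX-659/TEZ/IVA.

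**Completeness.** SAP numbering passes from 8.4.8 to 8.6, so text may have been removed. Nothing is inferred from that; the point is limited to SAP 8.4.4 and Table 11-6.

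It can also be said that an age split could be produced at reporting. It could, but the SAP does not commit to one, and listings are a poor substitute for a summary in a study of over 400 subjects.

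**Conclusion.** The concern holds in a limited form. As planned, the weight-gain percentages count expected growth together with other gain, mainly at the 5% level and often at 10%, in subjects followed long enough. The weight-loss percentages do not register an adolescent who stops gaining. In Part B the retained Part A baseline adds to the first problem.

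The individual figures (6.7% to 23% at Week 96, about 1.7% to 5.8% at Week 24) rest on assumed weights and growth rates. The effect on the pooled percentages is unknown because the number of growing subjects is not stated; 15 to 30 points is at most an upper bound under the assumed share. This is an inexpensive improvement to how the weight tables can be read. It does not affect the validity of any test, because none is planned.

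**What to change.** In SAP 8.4.4, tabulate the Table 11-6 weight thresholds and the weight and BMI change separately for growing subjects and adults, within each part. Either under 18 versus 18 and over at baseline, or the age-21 cut already used for height, would serve; the choice should be stated in advance.

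For the younger group, add change from baseline in weight-for-age, height-for-age and BMI-for-age z-scores, up to the upper age of the reference used, and name that reference. Height-for-age is needed because height is collected and has analysis windows in Appendix A but is not in the 8.4.4 summary list. State in the text that the split removes expected growth from the summary and does not attribute the remaining change to study drug.

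The cost is extra table columns and one derivation. Age, sex, height and weight are already collected, and SAP section 3 allows amendment before the database lock. The downside is smaller groups in each table, most of all in Part B.

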## Appendix E: Adverse Events of Special Interest

Table 11-7 MedDRA Preferred Terms for Event of Special Interest	
Adverse event of special interest	MedDRA preferred terms
Elevated transaminases	Alanine aminotransferase abnormal, Alanine aminotransferase increased, Aspartate aminotransferase abnormal, Aspartate aminotransferase increased, Transaminases abnormal, Transaminases increased, Liver function test abnormal, Liver function test increased, Hypertransaminasaemia, Hepatic enzyme abnormal, Hepatic enzyme increased
Rash	Rash, Rash erythematous, Rash macular, Rash maculo-papular, Rash maculovesicular, Rash vesicular, Rash pruritic, Rash follicular, Rash pustular, Nodular rash, Drug eruption, Fixed eruption, Urticaria, Urticaria papular, Urticaria vesiculosa, Urticarial dermatitis, Rash morbilliform, Rash papular, Rash papulosquamous, Rash rubelliform, Rash scarlatiniform , Drug hypersensitivity, Type IV hypersensitivity reaction, Dermatitis, Dermatitis atopic, Epidermolysis, Skin toxicity, Dermatitis allergic, Dermatitis exfoliative, Dermatitis exfoliative generalised, Erythema multiforme, Exfoliative rash, Mucocutaneous rash, Acute generalised exanthematous pustulosis, Cutaneous vasculitis, Urticarial vasculitis, Dermatitis bullous, Drug reaction with eosinophilia and systemic symptoms, Epidermal necrosis, Oculomucocutaneous syndrome, Skin exfoliation, Skin necrosis, Stevens-Johnson syndrome, Toxic epidermal necrolysis, Toxic skin eruption, Perioral dermatitis, Vasculitic rash, Immune-mediated dermatitis, Penile rash, SJS-TEN overlap, Erythrodermic atopic dermatitis, Scrotal rash

Note: The preferred terms listed in the table is based on the MedDRA version applicable at the time of finalization of the SAP. If the MedDRA version is upgraded at the time of the final analysis, the corresponding preferred terms based on the upgraded version, including adding, removing and renaming the preferred terms, will be used in the analysis of adverse events of special interest.

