##### **13.1.1.2 Clinically Significant Assessments**

Study assessments including laboratory tests, ECGs, PEs, and vital signs will be assessed and those deemed to have clinically significant worsening from baseline will be documented as an AE. When possible, a clinical diagnosis for the study assessment will be provided, rather than the

abnormal test result alone (e.g., urinary tract infection, anemia). In the absence of a diagnosis, the abnormal study assessment itself will be listed as the AE (e.g., bacteria in urine or decreased hemoglobin).

An abnormal study assessment is considered clinically significant if the subject has 1 or more of the following:

- Concomitant signs or symptoms related to the abnormal study assessment
- Further diagnostic testing or medical/surgical intervention
- A change in the dose of study drug or discontinuation from the study

Repeat testing to determine whether the result is abnormal, in the absence of any of the above criteria, does not necessarily meet clinically significant criteria. The determination of whether the study assessment results are clinically significant will be made by the investigator.

A laboratory value that is Grade 4 will not automatically be an SAE. A Grade 4 laboratory value will be an SAE if the subject's clinical status indicates a life-threatening AE.

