### **13.1.1.3 Documentation of Adverse Events**

All AEs will be collected from the time the ICF is signed until the subject completes study participation, as defined in Section 9.1.5.

All subjects will be queried, using nonleading questions, about the occurrence of AEs at each study visit. When possible, a constellation of signs and/or symptoms will be identified as 1 overall event or diagnosis. All AEs for enrolled subjects will be recorded in the CRF and source document. The following data will be documented for each AE:

- Description of the event
- Classification of "serious" or "nonserious"
- Date of first occurrence and date of resolution (if applicable)
- Severity
- Causal relationship to study drug(s)
- Action taken
- Outcome
- Concomitant medication or other treatment given

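### The SAP's Elevated transaminases event-of-special-interest row lists only laboratory-finding terms, so a transaminase rise recorded as a liver diagnosis under the protocol's own rule can fall outside that count

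*SAP*

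**What the plan says.** SAP Appendix E, Table 11-7, has two AESI rows, Elevated transaminases and Rash. The first opens with "Alanine aminotransferase abnormal, Alanine aminotransferase increased, Aspartate aminotransferase abnormal, Aspartate aminotransferase increased, Transaminases abnormal, Transaminases increased" and closes with "Liver function test abnormal, Liver function test increased, Hypertransaminasaemia, Hepatic enzyme abnormal, Hepatic enzyme increased". The note under the table says that, after a MedDRA upgrade, the updated terms "will be used in the analysis of adverse events of special interest". That confirms the list drives an AESI analysis; the note provides for changing the list only through a dictionary upgrade.

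The Rash row is built differently. Besides descriptive rash terms it holds severe diagnoses, for example "Skin necrosis, Stevens-Johnson syndrome, Toxic epidermal necrolysis, Toxic skin eruption".

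Protocol 13.1.1.2 governs how an abnormal assessment becomes an adverse event: "When possible, a clinical diagnosis for the study assessment will be provided, rather than the" abnormal test result on its own. The fallback follows: "In the absence of a diagnosis, the abnormal study assessment itself will be listed as the AE". Protocol 13.1.1.3 adds: "When possible, a constellation of signs and/or symptoms will be identified as 1 overall event or diagnosis".

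**The concern.** The analysis list and the recording rule pull in opposite directions. The list finds a transaminase event only if it carries a test-abnormality term. The rule makes that term second choice. A rise reported as ALT increased is counted; a rise that the site attributes to drug-induced liver injury or hepatitis and records that way is not, although transaminases rose in both subjects.

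At stake is one of only two AESIs in a study whose sole objective is long-term safety. If the missed cases are mainly those that were investigated, the AESI figure would under-represent the events a reader most wants it to show.

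**Working it through.** **1. The plan's only design figure.** SAP 6.2 and Protocol 12.1 state that with over 400 subjects and no events in a preferred term, a frequency above 1% is excluded with 95% confidence. With n = 400, P(0 events | 1%) = 0.99^400 = 0.018, below 0.05. The one-sided upper bound is 1 − 0.05^(1/400) = 0.746%; the two-sided bound is 1 − 0.025^(1/400) = 0.918%. The statement reproduces. It applies to single preferred terms, so the make-up of an AESI group does not alter it. The documents give no figure for the AESI count itself.

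**2. Term count.**

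| Row of Table 11-7 | Terms | Includes diagnoses? |
|---|---|---|
| Elevated transaminases | 11 | No: 10 are worded as abnormal or increased, and the eleventh, Hypertransaminasaemia, names the same finding |
| Rash | 52 | Yes, including Stevens-Johnson syndrome and toxic epidermal necrolysis |

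The transaminase row has no hepatitis, liver injury, hepatic failure, jaundice or bilirubin term.

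**3. Following one case through.** A subject's ALT rises and the finding is judged clinically significant.
- No diagnosis is reached: the event is the test abnormality, its term is in the row, and it is counted.
- A diagnosis is reached and recorded alone: its term is outside the row, and it is not counted.
- A diagnosis is recorded together with a separate transaminase event: it is counted through the second event.

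Only the second path loses a case. Protocol 13.1.1.2 leads to it whenever a diagnosis is available and the site does not also record the test finding.

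**4. Which cases take that path.** Protocol 9.8.1 requires a search for causes once an interruption criterion is met (ALT or AST above 8 × ULN, above 5 × ULN for more than 2 weeks, or above 3 × ULN with bilirubin above 2 × ULN and/or clinical jaundice). Work-up makes a recorded diagnosis more likely. It is a reasonable inference that more marked cases are more affected; neither document states it.

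**5. Size, on assumed inputs.** Neither the event rate nor the share recorded as a diagnosis is in the documents. Assume 400 subjects, 10% with a transaminase-driven event (400 × 0.10 = 40), and 2% to 10% of those recorded only as a diagnosis.
- Missed: 40 × 0.02 = 0.8 to 40 × 0.10 = 4 subjects.
- Counted incidence: (40 − 0.8)/400 = 9.8% down to (40 − 4)/400 = 9.0%, against a true 10%.

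**6. Where a missed case still appears.**
- SAP 8.4.1: treatment-emergent event tables by system organ class and preferred term, including the Grade 3/4, related, serious, interruption, discontinuation and fatal tables, and the subject listing for these categories other than related events.
- SAP 8.4.2 and Appendix D: ALT and AST bands up to above 20 × ULN, the combined criterion of ALT or AST above 3 × ULN with bilirubin above 2 × ULN, shifts from baseline, and scatter plots of maximum ALT and AST against maximum bilirubin. These use measured values and do not depend on event wording.

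**The case against.** The strongest reply is that the row does what its label says. It is called Elevated transaminases, not hepatic events, and a list of test terms fits a laboratory concept. The protocol's liver rules rest mainly on multiples of ULN, whereas its rash rules use grade and seriousness, which may explain why one row lists test terms and the other clinical entities. This stands in part: the plan never promises a general liver AESI, and jaundice or hepatic failure is a wider concept than a transaminase rise. It does not remove the mismatch, because a transaminase rise recorded under a diagnosis is missed even by the narrow concept.

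The recording rule is also softer than it may first appear. It applies only where a diagnosis is possible, it speaks of not giving the test result alone, and Protocol 13.1.1.3 concerns signs and symptoms rather than laboratory findings. A site may record both events. This stands, so cases can be lost; it does not follow that they will be.

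The outputs in step 6 answer most of the worry about hidden cases. They are not a full substitute. Preferred-term tables spread diagnoses over separate lines with no readable row that totals them, and threshold tables carry no seriousness or causality. Protocol 11.4.2 and the COVID-19 addendum allow local laboratory results in some circumstances, and the SAP does not say whether those enter the threshold analysis.

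A reader might infer that the serious liver cases drop out and that the liver safety conclusion is therefore biased towards benign. The documents do not support this. The text describing the AESI analysis cannot be read in the available SAP (the contents show a gap between 8.4.8 and 8.6, which is not counted as an error), so it is unknown whether that analysis reports seriousness or discontinuation, or whether any conclusion rests on it. Nor can a large loss among serious cases be claimed. Assuming 4 to 8 serious or treatment-stopping events, with every missed case among them, gives 1/8 to 4/4, or about 12% to 100%. Every input is assumed, and the top end pairs the most missed cases with the smallest subset.

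**Conclusion.** The point holds as a definitional mismatch limited to one summary. All 11 terms are laboratory findings, and the protocol makes such terms the fallback, so the AESI count can miss transaminase elevations recorded only as a liver diagnosis. On the assumed inputs the effect on overall AESI incidence is small, 0.2 to 1.0 percentage points out of 10%; the true number is unknown. That worked-up cases are the most affected is plausible but not shown. The cases remain visible elsewhere in the report, and no bias in the overall liver conclusion is established. This is a cheap improvement, worth making because safety is the study's only objective and this is one of its two AESIs.

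**What to change.** Amend SAP Table 11-7 before database lock, as SAP Section 3 allows:
- Keep the 11-term row for comparability with other studies of the drug, and label it as laboratory-finding terms only.
- Add a prespecified supplementary row, *Elevated transaminases or hepatic injury diagnosis*, holding the 11 terms plus hepatic-injury diagnosis terms, for example drug-induced liver injury, hepatotoxicity, liver injury, hepatocellular injury, the hepatitis terms, hepatic failure and jaundice.
- Count each subject once in the wider row, and read the liver AESI result from both rows.

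If lock has passed, SAP Section 3 has changes documented in the clinical study report, and the wider row should then be marked as added after lock. The cost is an appendix edit and one more row, with no new data. The downside is that a few diagnoses with another cause, such as viral hepatitis, may enter the wider row; these can be footnoted. Fixing the terms before the cases are reviewed avoids a post hoc choice.
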